## 9.2 Adverse Event Severity

The intensity of an AE is an estimate of the relative severity of the event made by the investigator based on his or her clinical experience and familiarity with the literature. The following definitions are to be used to rate the severity of an AE:

- Mild: The symptom is barely noticeable to the subject and does not influence performance of daily activities. Treatment is not ordinarily indicated.
- Moderate: The symptom is sufficiently severe to make the subject uncomfortable, and performance of daily activities is influenced. Treatment may be necessary.
- Severe: The symptom causes severe discomfort, and daily activities are significantly impaired or prevented. Treatment may be necessary.

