### **5.3 Discontinuations**

Subjects have the right to withdraw from the study at any time for any reason without penalty. The investigator also has the right to withdraw subjects from the study if he or she feels it is in the best interest of the subject or if the subject is uncooperative or noncompliant.

Should a subject decide to withdraw, all efforts will be made to complete and report the observations as thoroughly as possible, particularly the follow-up examination.

The investigator or one of his or her staff members should contact the subject to determine as completely as possible the reason for the withdrawal. A complete final evaluation at the time of the subject's withdrawal should be made with an explanation of why the subject is withdrawing from the study. If the reason for removal of a subject is an AE or an abnormal laboratory test result, the principal specific event or test will be recorded. The criteria for enrollment must be followed explicitly. Subjects who discontinue the study after taking his or her first dose will be asked, if they agree, to come for a last assessment (early termination visit). Subjects who discontinue will not be replaced.

Reasons for discontinuation include the following:

- The investigator decides that the subject should be withdrawn. If this decision is made because of a serious adverse event (SAE), the study product is to be discontinued immediately and appropriate measures are to be taken. The investigator will notify the sponsor immediately.
- The attending physician requests that the subject be withdrawn from the study.
- The subject, for any reason, requires treatment with another therapeutic agent that has been demonstrated to be effective for treatment of the study indication. In this case, discontinuation from the study occurs immediately upon introduction of the new agent.
- The subject is lost to follow-up. In this case, a reasonable attempt to contact the subject and ascertain his or her status must be made, and these attempts must be documented.
- The sponsor or regulatory authorities, for any reason, stop the study. In this case, all subjects will be discontinued from the study and notified of the reasons for the discontinuation.
- The subject has become pregnant at any time during the study.
- Other: the subject may withdraw from the study for any other reason, including withdrawal of consent.

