#### 6.2.7 Safety Monitoring Rules

If a severe AE or SAE is reported in any dose cohort, the study may be suspended pending review of the safety data or unless the investigator determines that the event is unrelated to the study product.

The sponsor, in consultation with the investigator(s), may decide to stop or modify the dose escalation at any time for safety reasons following review of study data.

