## **8.3 Safety Assessments**

#### 8.3.1 Vital Signs

The following vital signs will be recorded at every visit with the subject in a seated position, after having sat calmly for at least 5 minutes: systolic and diastolic blood pressure (mmHg), pulse (bpm), and body temperature (°C).

Weight (kg) and height (cm) will be collected to calculate the Body Mass Index (BMI) which will be recorded at the screening and baseline (Day 0) visits. The height will only be recorded once at the screening visit and the same value will be used for BMI calculation at baseline (Day 0). The weight will be recorded at screening, baseline (Day 0), and at the Week 12 visit (end of treatment visit).

If deemed appropriate by the investigator, clinically significant findings in the vital signs will exclude a subject from study participation. Any abnormal finding related to vital signs that the investigator considers to be clinically significant must be recorded as an AE if this abnormality was not present at the baseline (Day 0) visit or is assessed as having worsened since baseline (Day 0). Any change in health between the informed consent form and the first study drug administration will be recorded as medical history.

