#### 8.3.2 Physical Examination

The following sites/systems will be included in the physical examination to be performed at the visits specified in Section 7. In case clinically significant findings are detected at Week 12, the physical examination may be repeated at Week 16. Each system will be scored as normal/abnormal

(nonclinically significant or clinically significant). Pertinent details must be recorded for any clinically significant findings.

- General appearance
- Dermatological (except psoriasis)
- Head, eyes, ears, nose, throat (HEENT)
- Respiratory
- Cardiovascular
- Abdominal
- Neurological
- Musculoskeletal
- Lymphatic

If deemed appropriate by the investigator, clinically significant findings in the physical examination will exclude a subject from study participation. Any significant change will be reported as an AE if this abnormality was not present at the baseline (Day 0) visit or is assessed as having worsened since baseline (Day 0). Any change in health between the informed consent form and the first study drug administration will be recorded as medical history.

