#### 8.3.4 *Electrocardiogram*

Twelve-lead ECGs will be performed as a safety assessment at the visits specified in Section 7. In case clinically significant findings are detected at Week 12, the ECG may be repeated at Week 16. Clinically significant findings in the ECG will exclude a subject from study participation (as deemed appropriate by the investigator). Any significant change will be reported as an AE if this abnormality was not present at baseline (Day 0) visit or is assessed as having worsened since baseline (Day 0).

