## **9 ADVERSE EVENTS**

An AE is any untoward medical occurrence in a subject administered a pharmaceutical product, without regard to the possibility of a causal relationship with this treatment.

Investigators are responsible for monitoring the safety of subjects who are participating in this study and for alerting the sponsor of any event that seems unusual, even if this event may be considered an unanticipated benefit to the subject. The investigator is responsible for appropriate medical care of subjects during the study.

The investigator remains responsible for following through with an appropriate health care option for all AEs that are serious or that caused the subject to discontinue before completing the study. The subject should be followed until the event is resolved or stable. Follow-up frequency is left to the discretion of the investigator.

Safety will be evaluated by collecting information on AEs and by accessing data from vital signs, ECGs, physical examinations, and laboratory results.

Prior to subject enrollment, study site personnel will note the occurrence and nature of each subject's medical condition(s) in the appropriate section of the source document and CRF. During the study, site personnel will again note any change in the condition(s) and the occurrence and nature of any AEs.

If a subject experiences an AE at any time after the first dose of the study product, the event will be recorded as an AE in the source document and CRF.

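### The only AE severity scale (9.2) is worded around symptoms, so read literally a large but silent laboratory, ECG or vital-sign AE cannot be Severe and misses the severe-AE trigger in 6.2.7; the effect is small

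*Protocol*

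**What the plan says.** Section 9.2 first calls intensity an estimate by the investigator, drawing on clinical experience and the literature. It then fixes how the estimate is made: "The following definitions are to be used to rate the severity of an AE". Three grades follow (Mild, Moderate, Severe), each describing a symptom and its effect on the subject. The top grade is "Severe: The symptom causes severe discomfort, and daily activities are significantly impaired or prevented".

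Section 8.3 creates AEs from objective findings:

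- 8.3.1: "Any abnormal finding related to vital signs that the investigator considers to be clinically significant must be recorded as an AE", if the abnormality is new or worse since baseline.
- 8.3.2: "Any significant change will be reported as an AE if this abnormality was not present at the baseline (Day 0) visit", or has worsened since. Section 8.3.3 applies the same rule to laboratory tests.
- 8.3.4: "Any significant change will be reported as an AE if this abnormality was not present at baseline (Day 0) visit", or has worsened since.

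The grade is used in 6.2.7: "If a severe AE or SAE is reported in any dose cohort, the study may be suspended pending review of the safety data". That sentence makes an exception for events that the investigator judges unrelated to the product. Section 15.4 also uses the word severe, in a rule against dosing the remaining cohorts at higher doses. That rule covers the sentinel cohort only, accepts clinically significant as an alternative to severe, and requires the event to be possibly drug-related.

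**The concern.** Scheduled chemistry, haematology and ECG tests exist largely to find changes that a subject does not feel. The protocol makes such changes AEs and then grades them by discomfort and interference with daily life. A marked rise in ALT, AST or creatinine, or a marked neutropenia, may cause neither when it is found. All four are covered by the panels in Table 3, which are scheduled at Weeks 4, 8 and 12 of treatment.

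Section 6.2.7 is the protocol's named safety-monitoring rule for every cohort, at doses that may reach 1000 mg/d, the previously determined maximum tolerated dose. For an AE that is not serious, the grade alone decides whether the event falls under that rule. If the scale cannot express the size of a silent abnormality, the severe-AE part of the rule does not work for that class of event. Two investigators could also grade the same finding differently, one following the definitions and the other following clinical judgement.

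**Working it through.** The plan gives no figure to reproduce, and no formula applies. The check traces a silent abnormality through the text.

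**Step 1: does it become an AE?** Yes. All 4 of the sections 8.3.1 to 8.3.4 make a significant new or worsened finding an AE, and none of the 4 requires a symptom.

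**Step 2: how is it graded?** The scale has 3 grades. All 3 are worded around a symptom, and 0 of 3 refer to the size of an abnormality.

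| Element in 9.2 | Applied to a large, silent ALT rise |
|---|---|
| Severe, first condition: severe discomfort | not met |
| Severe, second condition: daily activities significantly impaired or prevented | not met |
| Remark on treatment | identical for Moderate and Severe, so it does not separate them |

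The two conditions for Severe are joined by *and*, so both would have to be met. Neither is. The nearest grade is Mild, and even that presupposes a symptom.

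**Step 3: which rules use the grade?** There are 2.

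| Rule | Cohorts | AE that meets it | Consequence |
|---|---|---|---|
| 6.2.7 | any | severe AE, or SAE | study may be suspended pending review |
| 15.4 | sentinel only | severe or clinically significant AE, possibly drug-related | remaining cohorts are not dosed at higher doses |

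In 15.4 the alternative wording catches a silent finding whatever its grade. In 6.2.7 there is no such alternative, so in 1 of the 2 rules the grade alone can decide whether a non-serious AE qualifies.

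**Step 4: which routes do not depend on the grade?**

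- The study may be stopped or interrupted at any time for safety reasons (4 and 6.2.6), and the second paragraph of 6.2.7 allows escalation to be stopped or modified at any time.
- The safety meeting before each next cohort judges intolerance from AEs and also from vital signs, examination, laboratory and ECG findings (4).
- Section 9.3 lets important medical events be treated as serious by judgement, which brings them under the SAE part of 6.2.7.
- The investigator may withdraw a subject. Section 5.3 foresees the case: "If the reason for removal of a subject is an AE or an abnormal laboratory test result".
- Section 9 makes the investigator responsible for "alerting the sponsor of any event that seems unusual".
- Ongoing data reviews (10.2.4) and a signed dose decision before escalation (15.4) remain in place.

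**Step 5: does the grade enter the analysis?** No. Section 10.2.3 plans the incidence of treatment-emergent and drug-related treatment-emergent AEs. The number of planned summaries by severity is 0.

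**The case against.** The strongest reply is that the severe-AE part of 6.2.7 confers no power the study lacks elsewhere. It only permits suspension, and sections 4 and 6.2.6 permit interruption at any time with no grade required. Silent findings also reach every dose decision as data, because the safety meeting looks at the laboratory, ECG, vital-sign and examination results themselves. This stands, and it is why the point is minor.

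A second reply is that 9.2 opens with the investigator's own estimate, which gives some basis for rating a large ALT rise as severe. This stands in part. The next sentence prescribes the definitions, so the text pulls both ways; removing that ambiguity is worth a paragraph.

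A third reply concerns the examples. Section 9.3 lists blood dyscrasias, in the context of intensive treatment, among events usually considered serious, so some neutropenias would enter 6.2.7 as SAEs. The protocol does not attribute the laboratory examples to this drug. Both remarks are fair. An abnormality that receives no such treatment is not plainly covered by those examples, and the serious-event route rests on judgement.

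A reader might infer more: that a dangerous silent toxicity would go unnoticed, or that dosing would have to continue. The routes above do not support that. A reader might also suppose that better grading would reveal QTc prolongation, the silent risk named in 15.4, at an earlier time. It would not, because the only ECG scheduled during treatment is at Week 12.

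**Conclusion.** The point holds as a minor fault in wording. The protocol creates a class of AEs that its only severity scale cannot grade sensibly, and that scale defines a trigger word in the any-cohort safety rule. The conclusion rests on reading 9.2 literally, with its definitions binding. An investigator who relies on the opening sentence of that section could reach a different grade.

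The practical effect is small. What is lost is the reliable working of one named, discretionary trigger for non-serious silent findings; no power to act is lost. The document allows no estimate of how many events would be affected or of any delay. A reader might infer that the safety results would be distorted, but the planned incidence summaries do not use the grade, and the primary endpoint, sample size and efficacy analyses are untouched.

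**What to change.** **Section 9.2.** Grade AEs that are laboratory, ECG, vital-sign or other objective findings by the size of the abnormality on a standard toxicity scale such as CTCAE. Include asymptomatic examination findings where the scale has criteria for them. Keep the present three definitions for symptomatic events.

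**Section 6.2.7.** State that grade 3 or higher on that scale counts as severe. Leave suspension discretionary and keep the exception for unrelated events.

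Adding clinically significant to 6.2.7 is a less suitable repair. Under 8.3.1 a vital-sign finding must already be clinically significant to be an AE, so every such AE would become a trigger. If alignment with 15.4 is wanted, its possibly-drug-related condition should come across too.

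**Cost.** One paragraph in 9.2, one sentence in 6.2.7 and one CRF completion instruction, with no new test or visit. The downside is that a few more events may need review; the number cannot be derived from the protocol, and no pause is forced.

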## 9.3 Serious Adverse Events

If a subject experiences an SAE at any time after the first study product administration, the event will be recorded as an SAE in the source document and CRF.

A serious adverse event or reaction is any untoward medical occurrence that, at any dose:

- Results in death
- Is life-threatening
- Requires in-patient hospitalization or prolongation of existing hospitalization
- Results in persistent or significant disability/incapacity
- Is a congenital anomaly/birth defect

NOTE: The term “life-threatening” in the definition of “serious” refers to an event in which the subject was at risk of death at the time of the event; it does not refer to an event that hypothetically might have caused death if it were more severe.

Medical and scientific judgment should be exercised in deciding whether expedited reporting is appropriate in other situations, such as important medical events that may not be immediately life-threatening or result in death or hospitalization, but may jeopardize the subject or may require intervention to prevent one of the other outcomes listed in the definition above. These should also usually be considered serious.

Examples of such events are intensive treatment in an emergency room or at home for allergic bronchospasm, blood dyscrasias, or convulsions that do not result in hospitalization; or development of drug dependency or drug abuse.

### **9.3.1 SAE Reporting**

All SAEs, related to the experimental treatment or not, occurring during the course of the study must be reported on an SAE form to the sponsor within 24 hours of the knowledge of the occurrence. (This refers to any AE that meets one or more of the aforementioned serious criteria.) The SAE reporting period ends at the Follow-up visit (Week 16).

Reporting should be done by sending the completed SAE Report Form to the following e-mail address (faxing can also be done as a second option in case e-mailing is not possible).

Contact name: [name]  
Department of Dermatology, Aarhus University Hospital  
[name]  
Denmark  
E-mail: [[contact]](mailto:[contact])  
[contact]  
[contact]

The sponsor will evaluate all SAEs as soon as the reports are received and will assess the expectedness of each SAE in relation to the study treatment. For each SAE received, the sponsor will make a determination as to whether the criteria for expedited reporting to relevant regulatory authorities have been met. The sponsor or designee will manage the expedited reporting of relevant safety information to concerned regulatory agencies in accordance with local laws and regulations.

### **9.4 Pregnancy Reporting**

If a female subject or a female partner of a male subject becomes pregnant during the study, the subject should inform the study site as soon as possible. Upon confirmation of the pregnancy, the female subject will be discontinued from the study. The investigator must complete a study-specific pregnancy form upon confirmation of a pregnancy and send it to the sponsor within 24 hours of confirmation of the pregnancy (contact information to be used is the same as for SAE reporting). Posttreatment follow-up should be done to ensure subject safety. Pregnancy is not itself an AE or SAE; however, maternal/fetal complications or abnormalities will be recorded as AEs or SAEs, as appropriate. The investigator will follow the pregnancy until completion or until pregnancy termination and, in the case of a live-born offspring, to 1 month of age in that infant. The investigator will notify the sponsor of the outcome as a follow-up to the initial pregnancy form. All pregnancies should be reported to the sponsor and ethics committee.

### **9.5 Suspected Unexpected Serious Adverse Reactions**

If a subject experience a SUSAR at any time after the first study product administration, the event will be recorded as a SUSAR in the source document and CRF.

SUSARs meets the same criteria as SARs, but are not expected to occur according to the reference safety informations in the Investigator's Brochure.

#### **9.5.1 SUSAR Reporting**

All SUSARs occurring during the course of the study must be reported on a SUSAR form to the sponsor within 24 hours of the knowledge of the occurrence.

Reporting should be done by sending the completed SUSAR Report Form to the following e-mail address (faxing can also be done as a second option in case e-mailing is not possible).

Contact name: [name]  
Department of Dermatology, Aarhus University Hospital  
[name]  
Denmark  
E-mail: [[contact]](mailto:[contact])  
[contact]  
[contact]

Sponsor must ensure that all relevant information about SUSARs, which is fatal or life threatening, is recorded and reported to Danish Medicines Agency and the Ethical Committee no later than 7 days after sponsor has been informed about such a serious reaction. No later than 8 days after initial reporting sponsor must inform the Danish Medicines Agency and the Ethical Committee about follow-up information and action taken.

Any other SUSARs must be reported to Danish Medicines Agency and the Ethical Committee no later than 15 days after sponsor has been informed about them.

SUSAR's from non-EU/EEA countries shall not be reported to the Danish Medicines Agency.

## 10 SAMPLE SIZE AND STATISTICAL METHODS

### 10.1 Determination of Sample Size

No formal sample size calculations were conducted. Six subjects will be enrolled into each cohort, for a total of maximum 16 subjects. This sample size was selected to allow sufficient characterization of the drug's safety profile over the planned doses range and to allow for preliminary efficacy assessments of CUDC-305 in subjects with moderate to severe plaque psoriasis.

### 10.2 Statistical and Analytical Plans

Because of the nature and design of the study, the statistical analysis will be mainly descriptive.

Descriptive summaries of demographics, baseline characteristics, and subject disposition will be presented by dose regimen and overall. Continuous variables will be summarized by dose regimen and overall in tables and will include the number of subjects, mean, standard deviation, median, minimum, maximum, and range. Categorical variables will be presented by dose regimen and overall in tables as frequencies and percentages.

Even if not sample size calculation was performed we bring a power analysis for the primary endpoint: PASI at week 12. A non parametric Wilcoxon signed-rank test will allow us to determine that Change in PASI is significant different form 0 with 80% power and 95% confidence level if the observed effect size is greater or equal to 1.23 standard deviation.

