## SUMMARY

**Title:** A Phase 1b, open-label, singlecenter, single-arm, dose-selection, proof-of-concept study to assess the safety and efficacy of a novel HSP90 inhibitor (CUDC-305) in the treatment of moderate to severe plaque psoriasis

**Phase:** 1b

**Population:** Approximately 12 and not exceeding 16 male or female subjects aged 18 years or older with moderate to severe plaque psoriasis will be included in this study.

**Number of Sites:** One center in Denmark will participate in this study.

**Study Duration:** Subject participation will be approximately 20 weeks, involving a 4-week screening phase, a 12-week treatment phase, and a 4-week observational follow-up phase to assess for psoriasis relapse and flare.

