**Overall Study Design:**

This is a 12-week treatment, singlecenter, open-label, single-arm, dose-selection, proof-of-concept study to determine a dosage of CUDC-305 that is tolerable and demonstrates preliminary efficacy for use in future efficacy Phase 2 trials.

Eligible subjects will be sequentially assigned to one of the four cohorts (approximately n = 4 per cohort) receiving ascending or descending doses of CUDC-305. The first cohort will be administered a starting oral dose of 250 mg/d for 12 weeks, which is believed to be the target effective dose for treatment of psoriasis. The dose regimen to be administered to the subsequent cohort will be decided after reviewing the safety and efficacy data of the first four subjects completing the treatment period (12 weeks) in the current cohort. A safety meeting will take place to review the available data prior to deciding the next dose and then initiating dosing of the subsequent cohort. The doses that will be evaluated in this study range between 100 mg and 1000 mg and may include: 100 mg, 250 mg, 500 mg, 800 mg, or 1000 mg orally once daily.

The sponsor and principal investigator(s) will jointly evaluate the safety and tolerability of CUDC-305 at the safety meeting, and intolerance will be determined by taking into account all information from adverse events (AEs), vital signs, physical examination findings, laboratory abnormalities, and electrocardiogram (ECG) findings. The study may be stopped permanently or interrupted at any time for safety reasons.

PASI, PGA, BSA, pruritus NRS, and DLQI will be performed to assess efficacy. Safety will be assessed with the vital signs, physical examination, clinical laboratory tests, ECG, and collection of AEs.

Skin biopsies will be collected from nonlesional and lesional skin for immunohistochemistry and gene expression analysis.

Medical photographs of the target lesion will also be performed at each study visit (except the screening visit).

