### **Statistical Analysis:**

Because of the nature and design of the study, the statistical analysis will be mainly descriptive.

Descriptive summaries of demographics, baseline characteristics, and subject disposition will be presented by dose regimen and overall. Continuous variables will be summarized by dose regimen and overall in tables and will include the number of subjects, mean, standard deviation, median, minimum, maximum, and range. Categorical variables will be presented by dose regimen and overall in tables as frequencies and percentages.

No formal sample size calculations were conducted. Four subjects will be enrolled into each cohort, for a total of a maximum of 16 subjects. This sample size was selected to allow sufficient characterization of the drug's safety profile over the planned doses range and to allow for

preliminary efficacy assessment of CUDC-305 in subjects with moderate to severe plaque psoriasis.

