## **2 STUDY OBJECTIVES**

### **2.1 Primary Objective**

The primary objective is as follows:

- To determine the optimal efficacious dose-range of CUDC-305 in the treatment of moderate to severe plaque psoriasis in a Phase 1b proof-of-concept study

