## 5 STUDY POPULATION

This study will include approximately 16 subjects with moderate to severe plaque psoriasis. Subjects will be men or women, aged 18 years or older.

Subjects who are discontinued after taking the first dose of study product will not be replaced.

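### The 80% power at 1.23 SD names no sample size and cannot hold in a dose cohort of four; the cohort size is itself given as both six and four

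*Protocol*

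**What the plan says.** Section 10.2 calls the analysis mainly descriptive and then offers a power statement for the primary endpoint, change in PASI at Week 12. A signed-rank test is said to show a change different from zero "with 80% power and 95% confidence level if the observed effect size is greater or equal to 1.23 standard deviation". The sentence gives no number of subjects, does not say whether the test is one- or two-sided, and does not say whether it is applied per dose or to all doses together. The same section plans both levels of summary: "Continuous variables will be summarized by dose regimen and overall in tables".

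The cohort size differs between sections:

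- Section 10.1: "Six subjects will be enrolled into each cohort, for a total of maximum 16 subjects".
- Summary, Statistical Analysis: "Four subjects will be enrolled into each cohort, for a total of a maximum of 16 subjects".
- Summary, Overall Study Design, repeated in Sections 4 and 6.2.6: "Eligible subjects will be sequentially assigned to one of the four cohorts (approximately n = 4 per cohort").

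The total also varies. The Summary gives "Approximately 12 and not exceeding 16 male or female subjects", while Section 5 states "This study will include approximately 16 subjects with moderate to severe plaque psoriasis".

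Section 10.2.2 rules out formal statistical comparison, although it allows doses to be compared. Section 10.2.4 permits changes from baseline to be tested with a mixed-effects model.

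**The concern.** The primary objective is about dose: "To determine the optimal efficacious dose-range of CUDC-305". A reader will therefore naturally take a power figure for the primary endpoint as applying within a dose. In a group of about four, a signed-rank test has so few possible outcomes that conventional significance may be out of reach, and the sentence would then promise 80% power where the test cannot reject. The reader cannot settle which n was meant, because the sentence gives none and the sections disagree on cohort size. In addition, power is a property of an assumed true effect, whereas the sentence attaches it to an observed one.

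At stake is the only power statement for the primary endpoint, and with it what a reader may conclude from a non-significant result at a given dose.

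**Working it through.** **Inputs.** Test, 80% power, 95% confidence level (alpha 0.05) and 1.23 SD come from Section 10.2. Candidate sizes are 4 (Summary, Sections 4 and 6.2.6), 6 (Section 10.1), and 12 and 16 (Summary, Section 5); 5 is added as a reading of approximately four. Assumption: changes are normal with a common shift of d SDs. Exact power comes from the exact null distribution with simulation.

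**1. Reproducing the stated figure.** Among 4, 6, 12 and 16, exact power at 1.23 SD is near 80% only at n = 6, one-sided. The test rejects when the negative-rank sum is at most 2, so its size is 3/64 = 0.047. Power is 0.797, and 80% is reached at 1.235 SD. A noncentral-t calculation with n multiplied by the signed-rank efficiency 3/π = 0.955 puts the 80% effect at 1.226 SD.

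This suggests a six-per-cohort origin but does not prove one, because cruder formulas also come close:

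- n = 6, two-sided z with efficiency 0.864: 2.8016/√(6 × 0.864) = 1.2305 SD.
- n = 4, one-sided plain z: 80% effect 1.243 SD, power 0.793 at 1.23 SD.

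These z formulas ignore the discreteness of the test.

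**2. Smallest attainable p-value.** Under the null all 2ⁿ sign patterns are equally likely, so the minimum is 1/2ⁿ one-sided and 2/2ⁿ two-sided.

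- n = 4: 1/16 = 0.0625 and 2/16 = 0.125.
- n = 5: 1/32 = 0.03125 and 2/32 = 0.0625.
- n = 6: 1/64 = 0.0156 and 2/64 = 0.03125.

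At n = 4 the exact test can never reach 0.05. The large-sample normal approximation without continuity correction gives 0.068 two-sided at n = 4, still above 0.05. Its one-sided value of 0.034 is below the exact 0.0625, so it is not valid at this size.

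**3. Exact power at 1.23 SD, alpha 0.05.**

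| n | One-sided | Two-sided | Effect for 80% power |
|---|---|---|---|
| 4 | 0 | 0 | none |
| 5 | 0.56 | 0 | 1.71 SD one-sided; none two-sided |
| 6 | 0.797 | 0.50 | 1.235 SD one-sided; 1.79 SD two-sided |
| 12 | 0.986 | 0.958 | about 0.94 SD two-sided |
| 16 | 0.998 | 0.993 | 0.78 SD two-sided |

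Closed-form check: where rejection requires every change to be in the same direction, power is essentially Φ(1.23)ⁿ. This gives 0.560 at n = 5 one-sided and 0.499 at n = 6 two-sided, matching the simulation.

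**4. Cohort arithmetic.** 6 × 4 = 24, which exceeds 16; 4 × 4 = 16. Six per cohort and four cohorts cannot both hold under the stated maximum.

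**5. Precision at four.** The 95% t-interval half-width for a mean change is t(0.975, 3)/√4 = 3.182/2 = 1.59 SD.

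**The case against.** The protocol never says that the signed-rank test is run per cohort. Summaries are planned overall as well as by dose, and on a pooled reading the statement is true, merely conservative. Nor is 1.23 SD baseless: it can be reproduced from six subjects, the number printed in Section 10.1. No formal sample size calculation was made, dose decisions rest on review of safety and efficacy data, and whether an optional test is run can be left to a statistical analysis plan.

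Much of this stands. The pooled reading is harmless, the figure is probably a consequence of an inconsistent n, and no enrolment number or decision rule depends on it.

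It does not remove the problem. Six per cohort conflicts with the Summary and Sections 4 and 6.2.6, and no section resolves the conflict. The sentence speaks of a change different from zero, which is two-sided wording; under an exact two-sided test, none of four, five or six per cohort gives 80% at 1.23 SD. Pooling rescues the power but does not separate the doses, which is what the primary objective asks. The allowance in Section 10.2.2 for comparing doses does not cover this one-sample test against zero. The point corrects a figure and a contradiction that the protocol itself prints, so it does not ask for detail that belongs in a later document.

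**Conclusion.** The point holds: the power sentence and the cohort size are wrong as written and should be fixed. At four per cohort the exact signed-rank test has zero power, one- or two-sided, whatever the effect. That result needs no distributional assumption beyond the test's own null. If approximately four means five, power at 1.23 SD is 0 two-sided and 0.56 one-sided. Pooled two-sided power is 0.958 at n = 12 and 0.993 at n = 16, so 1.23 SD is not the 80% effect there either. The non-zero powers assume normal changes, a common shift across doses when pooled, and every subject evaluable; Section 5.3 does not replace discontinued subjects, so evaluable numbers can only fall.

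The cohort-size contradiction (six against four; 24 against a maximum of 16) rests on the text alone. The practical consequence is moderate, because the analysis is mainly descriptive and nothing is sized on the figure.

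**What to change.** 1. Reconcile the cohort size in Section 10.1 with the Summary and Sections 4 and 6.2.6, and align the totals in the Summary and Section 5.
2. Delete the power sentence in Section 10.2, or restate it with n, sidedness, analysis unit and an assumed true effect. One consistent version is: pooled intent-to-treat population, two-sided alpha 0.05, 80% power at about 0.78 SD for 16 subjects or 0.94 SD for 12, with the common-shift assumption stated.
3. If four per cohort stands, say that a within-dose signed-rank test cannot reach 0.05, and report the change at each dose as an estimate with a 95% confidence interval (half-width about 1.59 SD at four subjects).
4. Align this with Sections 10.2.2 and 10.2.4 so that it is clear whether the signed-rank test will be run.

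The cost is protocol wording only: no added subjects, visits or procedures. Any implied claim of power at dose level is given up.
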